### ARRHYTHMIA

Any variation from the normal rhythm of the heartbeat, including sinus arrhythmia, premature beat, heart block, atrial fibrillation, atrial flutter and tachycardia.

- Major Arrhythmias: Complete heart block, ventricular tachycardia and ventricular fibrillation
- Serious Arrhythmias: Any arrhythmia requiring surgical or invasive intervention or DC cardioversion

### ATRIAL FIBRILLATION

Atrial fibrillation will be classified according to the International Consensus on Nomenclature and Classification of Atrial Fibrillation; A Collaborative Project of the Working Group on Arrhythmias and the Working Group on Cardiac Pacing of the European Society of Cardiology and the North American Society of Pacing and Electrophysiology, Europace 2003, Vol 5.

- **Paroxysmal:** spontaneous termination within 7 days and most often <48 hours
- **Persistent:** is not self-terminating; lasts longer than 7 days; or prior cardioversion
- **Permanent (accepted):** does not terminate, or terminated but relapsed; no cardioversion attempt

## BLEEDING EVENT

Bleeding event will be defined according to the Valve Academic Research Consortium (VARC)-2; Updated Standardized Endpoint Definitions for Transcatheter Aortic Valve Implantation (TAVI); 2012-10-09.

Life-threatening or Disabling Bleeding

 
• Fatal bleeding (BARC type 5) OR
 
• Bleeding in a critical area or organ, such as intracranial, intraspinal, intraocular, or pericardial necessitating pericardiocentesis, or intramuscular with compartment syndrome (BARC type 3b) OR
 
• Bleeding causing hypovolemic shock or severe hypotension requiring vasopressors or surgery OR
 
• Overt source of bleeding with drop in hemoglobin of <math>\geq 5</math> g/dL or whole blood or packed red blood cells (RBC) transfusion <math>\geq 4</math> units* (BARC type 3b)
 

Major Bleeding ( BARC type 3a )

 
• Overt bleeding either associated with a drop in the hemoglobin level of at least 3.0g/dL or requiring transfusion of 2-3 units of whole blood/RBC, or causing hospitalization or permanent injury or requiring surgery AND
 
• Does not meet criteria of life-threatening or disabling bleeding
 

Minor Bleeding ( BARC type 2 or 3a, depending on severity )

 
• Any bleeding worthy of clinical mention (eg. access site hematoma) that does not qualify as life-threatening, disabling or major
 

\* Given one unit of packed RBC typically will raise blood hemoglobin concentration by 1g/dL, an estimated decrease in hemoglobin will be calculated.  
BARC = Bleeding Academic Research Consortium

Life-threatening and Major bleeding events are considered to be serious.

## BUNDLE BRANCH BLOCK

ACC/AHA/HRS 2006 Key Data Elements and Definitions for Electrophysiological Studies and Procedures; A Report of the American College of Cardiology/ American Heart Association Task Force on Clinical Data Standards (ACC/AHA/HRS Writing Committee to Develop Data Standards on Electrophysiology), JACC, Vol. 48, No. 11, 2006.

### Left Bundle Branch Block (LBBB)

- QRS duration 120 ms or longer
- Delayed onset of intrinsicoid deflection in I, V5, and V6  $\geq 60$  ms
- Broad and notched or slurred R waves in I, aVL, V5, and V6
- rS or QS complexes in right precordial leads
- ST-segment and T waves in opposite polarity to the major QRS deflection

### Right Bundle Branch Block (RBBB)

- QRS duration  $\geq 120$  ms
- rsR $\equiv$  or rSR $\equiv$  complexes in V1 and V2
- Delayed onset of intrinsicoid deflection in V1 and V2  $\geq 50$  ms
- Broad, slurred S wave in I, V5,

Any new or worsening LBBB or RBBB that requires the placement of a permanent pacemaker and/or other surgical or invasive intervention will be considered to be serious.

## **CARDIAC PERFORATION**

A laceration or tearing of the walls of the ventricles or atria of the heart, of the interatrial or interventricular septum, of the papillary muscles or chordae tendineae or of the one of the valves of the heart.

Cardiac perforation events will be classified into additional subgroups according to the Valve Academic Research Consortium (VARC)-2; Updated Standardized Endpoint Definitions for Transcatheter Aortic Valve Implantation (TAVI); 2012-10-09

### **Mitral valve apparatus damage or dysfunction**

Angiographic or echocardiographic evidence of new damage (chordae papillary muscle, or to the leaflet) to the mitral valve apparatus or dysfunction (eg. opening restrictions due to the THV) of the mitral valve during or after the TAVI procedure.

### **Ventricular septal perforation**

Angiographic or echocardiographic evidence of a new septal perforation during or after the TAVI procedure.

## **CARDIAC TAMPONADE**

Clinical syndrome caused by the accumulation of fluid in the pericardial space, resulting in reduced ventricular filling and subsequent hemodynamic compromise.

## **CARDIOGENIC SHOCK**

Patient was, at the time of procedure, in a clinical state of hypoperfusion sustained for greater than 30 minutes, according to either of the following criteria:

1. Systolic BP < 80 and/or Cardiac Index < 1.8 despite maximal treatment; or
2. IV inotropes and/or IABP necessary to maintain Systolic BP > 80 and/or CI > 1.8

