#### C.3.6.2 Exclusion Criteria

Subjects are NOT eligible for trial participation if they meet ANY of the following exclusion criteria:

1. Subject has refused surgical aortic valve replacement (SAVR) as a treatment option;
2. Any condition considered a contraindication for placement of a bioprosthetic valve (i.e. subject requires a mechanical valve);

3. A known hypersensitivity or contraindication to all anticoagulation/antiplatelet regimens (or inability to be anticoagulated for the index procedure), nitinol, or sensitivity to contrast media which cannot be adequately pre-medicated;
4. Blood dyscrasias as defined: leukopenia (WBC <1000mm^3), thrombocytopenia (platelet count <50,000 cells/mm^3), history of bleeding diathesis or coagulopathy;
5. Ongoing sepsis, including active endocarditis;
6. Any condition considered a contraindication to extracorporeal assistance;
7. Any percutaneous coronary or peripheral interventional procedure performed within 30 days prior to randomization (Subjects with recent placement of drug eluting stent(s) should be assessed for ability to safely proceed with SAVR within the protocol timeframe);
8. Symptomatic carotid or vertebral artery disease or successful treatment of carotid stenosis within six weeks of randomization;
9. Cardiogenic shock manifested by low cardiac output, vasopressor dependence, or mechanical hemodynamic support;
10. Recent (within 6 months of randomization) cerebrovascular accident (CVA) or transient ischemic attack (TIA);
11. Active gastrointestinal (GI) bleeding that would preclude anticoagulation;
12. Subject refuses a blood transfusion;
13. Severe dementia (resulting in either inability to provide informed consent for the trial/procedure, prevents independent lifestyle outside of a chronic care facility, or will fundamentally complicate rehabilitation from the procedure or compliance with follow-up visits);
14. Multivessel coronary artery disease with a Syntax score >22 and/or unprotected left main coronary artery (Syntax score calculation is not required for patients with history of previous revascularization if repeat revascularization is not planned);
15. Estimated life expectancy of less than 24 months due to associated non-cardiac co-morbid conditions;
16. Other medical, social, or psychological conditions that in the opinion of the Investigator precludes the subject from appropriate consent or adherence to the protocol required follow-up exams;

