### **Surgical Considerations**

Surgical aortic valve replacement is typically performed with cardio-pulmonary bypass (CPB) on an arrested heart with a clamped aorta. Local practice and surgical standards should govern type of cardioplegia and the temperature/flow/pressure perfusion strategy as well as the activated clotting time used at either institution for safe CPB. Typically a minimum of 2 liters/m^2/minute with a systemic arterial blood pressure of 60mmHg during CPB should be maintained and possibly increased in the elderly patients.

Cannulation for isolated SAVR CPB should be ascending aorta for arterial return unless there is ascending aortic arteriosclerosis or dilatation (>4cm in diameter), and right atrial for venous drainage. Embolic devices are not routinely used in SAVR.

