#### C.5.1.4 Major Adverse Event

Major adverse event (MAE) includes:

- MACCE
- Acute kidney Injury
- Cardiac tamponade
- Prosthetic valve dysfunction
- Cardiogenic shock
- Prosthetic valve endocarditis
- Life-threatening, disabling or major bleeding
- Major vascular complication
- Cardiac perforation
- Valve malpositioning

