### C.6.8 Secondary Endpoints

#### C.6.8.1 Secondary Endpoints Compared Between TAVI and SAVR

1. Incidence of Major Adverse Cardiovascular and Cerebrovascular Events (MACCE) at 30 days, 6 months, 12 months, 18 months, 24 months, and annually thereafter up to 5 years. MACCE is defined as a composite of:

- All-cause death
- Myocardial infarction (MI)
- All stroke, and
- Reintervention (defined as any cardiac surgery or percutaneous reintervention catheter procedure that repairs, otherwise alters or adjusts, or replaces a previously implanted valve)

MACCE-incidence estimates will be provided for the two treatment groups at 30 days, 6 months, 12 months, 18 months, 24 months, and annually thereafter up to 5 years. The statistical method will be the Bayesian version of a comparison of proportions (with predictions).

Additionally, incidence of MACCE will be compared at 30 days or hospital discharge, whichever is later. The statistical method will be the Bayesian version of a comparison of proportions.

2. The occurrence of individual MACCE components at 30 days, 6 months, 12 months, 18 months, 24 months, and annually thereafter up to 5 years.

MACCE components will be summarized and their incidence estimates provided at 30 days, 6 months, 12 months, 18 months, 24 months, and annually thereafter up to 5 years. The statistical method will be the Bayesian version of a comparison of proportions (with predictions).

3. Major Adverse Events (MAE) and individual components at 30 days, 6 months, 12 months, 18 months, 24 months, and annually thereafter up to 5 years.

MAE events and individual components will be summarized and the incidence of MAEs will be provided at 30 days, 6 months, 12 months, 18 months, 24 months, and annually thereafter up to 5 years. The statistical method will be the Bayesian version of a comparison of proportions (with predictions).

Additionally, incidence of major vascular complications and incidence of major or life-threatening bleeding events at 30 days or hospital discharge, whichever is longer, will also be compared using the Bayesian version of a comparison of proportions.

4. Incidence of Early safety at 30 days defined as a composite of:

- All-cause mortality
- All stroke (disabling and non-disabling)
- Life-threatening bleeding
- Acute kidney injury—Stage 2 or 3 (including renal replacement therapy)
- Coronary artery obstruction requiring intervention
- Major vascular complication

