## **CORONARY OBSTRUCTION**

Valve Academic Research Consortium (VARC)-2; Updated Standardized Endpoint Definitions for Transcatheter Aortic Valve Implantation (TAVI); 2012-10-09.

Angiographic or echocardiographic evidence of a new, partial or complete, obstruction of a coronary ostium, either by the valve prosthesis itself, the native leaflets, calcifications, or dissection, occurring during or after the TAVI procedure.

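### Two O.2 definitions do not fit the endpoints that use them: cardiogenic shock is tied to the time of the procedure, and coronary obstruction is tied to TAVI only

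*Combined protocol and SAP*

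**What the plan says.** **Cardiogenic shock.** O.2 gives one definition. It opens "Patient was, at the time of procedure, in a clinical state of hypoperfusion sustained for greater than 30 minutes" and then requires either of two criteria on blood pressure, cardiac index or support. C.5.1.4 lists "Cardiogenic shock" among the MAE components, and the MAE entry in O.2 repeats it. Secondary endpoint 3 in C.6.8.1 is "Major Adverse Events (MAE) and individual components at 30 days, 6 months, 12 months, 18 months, 24 months, and annually thereafter up to 5 years", analysed by a Bayesian comparison of proportions between arms. C.6.11 treats MAE as a key secondary endpoint and examines it by gender, revascularization need and access route. Separately, exclusion criterion 9 in C.3.6.2 bars "Cardiogenic shock manifested by low cardiac output, vasopressor dependence, or mechanical hemodynamic support".

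**Coronary obstruction.** O.2 attributes its definition to VARC-2 and describes a new obstruction of a coronary ostium, "either by the valve prosthesis itself, the native leaflets, calcifications, or dissection, occurring during or after the TAVI procedure". Secondary endpoint 4 in C.6.8.1, early safety at 30 days, includes "Coronary artery obstruction requiring intervention". That composite is estimated for both treatment groups and compared by proportions.

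**Who applies the definitions.** Under C.5.3 the CEC classifies events by the definitions and processes in the protocol and in its own charter.

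**The concern.** Each definition is narrower than the endpoint it serves. The shock wording suits a baseline or operative descriptor, but the endpoint is an outcome followed for five years. The obstruction wording suits a single-arm TAVI report, but the endpoint is a randomized comparison.

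An adjudicator who follows O.2 faithfully will leave out events that a reader of the results would expect to be included. One who departs from O.2 will be using a counting rule that the protocol does not record. Allocation is not blinded (C.4.5), so event rules that work the same way in both arms matter more than usual. At stake is whether two between-arm safety results measure what their labels say.

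**Working it through.** The plan states no rate for either component, so there is no figure of its own to reproduce. Its sample size rests on the 17% primary-endpoint rate, and neither definition enters that calculation. The check is mainly a comparison of texts, with an illustration of size.

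**1. Timing of shock.**
- Definition: a state present at the time of the procedure.
- Endpoint: MAE components at 30 days and repeatedly to 5 years.
- Entry rule: exclusion 9 removes patients already in shock.
- Taken together, the component captures little beyond shock around the procedure. Shock starting on day 2 or in month 8 does not qualify, so the component cannot grow over follow-up.

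**2. Arm for obstruction.**
- Definition: during or after TAVI.
- Endpoint: 30-day composite in both TAVI and SAVR.
- A SAVR subject with the same finding and the same intervention does not meet the definition. The prosthesis itself, calcifications and dissection, all named in the definition, are not described there as particular to TAVI.

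**3. Is either repaired elsewhere?** Not in the text available for this check.
- O.2 times acute kidney injury and myocardial infarction from the index procedure, which covers both arms, so suitable wording already exists in the same section.
- The second analysis under VARC-I definitions (C.6.12.2) lists neither term.

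**4. Size for early safety (illustration).** The mITT sample is 1600, randomized 1:1 (C.6.5.2), or 800 per arm. Let q be the assumed proportion of SAVR subjects whose only early-safety event is an uncounted obstruction.
- Uncounted SAVR subjects = 800 × q. For q = 0.1% to 1.0% this is 0.8 to 8.
- The recorded SAVR rate is too low by q, so the TAVI minus SAVR difference is too high by q: 0.1 to 1.0 percentage points against TAVI.
- Standard error of the difference = √(2p(1−p)/800), where p is an assumed composite rate. At p = 10% it is √(2 × 0.10 × 0.90/800) = 0.015, so the shift is 0.07 to 0.67 standard errors.
- At q = 1.0% the shift is 0.92 standard errors for p = 5% (SE 0.0109) and 0.50 for p = 20% (SE 0.020).

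**5. Size for MAE (illustration).** Let q_T and q_C be the proportions in TAVI and SAVR with uncounted shock and no other MAE component. Counting them would change the TAVI minus SAVR difference by q_T − q_C:
- 1% and 1%: no change.
- 1% and 3%: −2 points.
- 3% and 1%: +2 points.

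**6. Component versus composite.** Suppose, as an assumption, that 1% to 4% of an arm develops shock by 30 days and one third to two thirds of it begins after the procedure. The component then loses 1% × 1/3 = 0.3 to 4% × 2/3 = 2.7 points in that arm. This bounds the loss to the MAE rate from above, because a subject who also dies, has a myocardial infarction or has another listed event already counts.

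**The case against.** Several counter-arguments have force.

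- **The events are still collected.** New or worsening adverse events are recorded through 24 months, and serious and cardiovascular events after that (C.5.2). This stands: the fault lies in endpoint classification and not in data capture.
- **The CEC charter may contain a working rule.** C.5.3 says the charter will set explicit rules. The charter and the other parts of the document were not available for this check, so what happens in practice is unknown. If such a rule exists, O.2 should state it.
- **The obstruction definition is credited to VARC-2, and its error works against the investigational device.** Both are true. The source explains the wording but does not make it fit a two-arm comparison, and an error unfavourable to the sponsor is still an error.
- **Neither composite supports a labeling claim.** This is correct. Neither is in the hierarchy in C.6.10.

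A reader might also infer that the shock wording leans against SAVR, because C.4.7.2 describes bypass "with a systemic arterial blood pressure of 60mmHg during CPB should be maintained" while the shock criteria use 80. The documents do not support that. The 60 mmHg is a systemic arterial pressure and is not stated to be systolic. The same sentence gives a flow of at least 2 liters/m²/minute, above the 1.8 cardiac index cut-off. The definition also requires a sustained clinical state of hypoperfusion, and its wording is the same for both arms.

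**Conclusion.** Both definitions are mis-specified as written, with different consequences.

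- **Cardiogenic shock** affects MAE only. It under-counts the component in both arms. It biases the between-arm difference only if shock-only rates differ, and the documents do not show in which direction.
- **Coronary obstruction** affects early safety only. It is one-sided, against TAVI, by 0.1 to 1.0 percentage points if 0.1% to 1.0% of SAVR subjects have it as their sole early-safety event. That range is an assumption.

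It would be tempting to conclude that the MAE and early-safety comparisons are therefore wrong. That goes too far. The size cannot be computed from the documents, any assumed component rate is only an upper bound on the shift in the composite, and the shift may be small. The primary endpoint, the sample size and the labeling hierarchy are unaffected. The conclusion rests on a literal reading of O.2. It is still worth correcting, because the literal reading misclassifies events and suitable wording already exists in the same section.

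**What to change.** In O.2:

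- Define the cardiogenic shock endpoint as new onset during or after the index procedure through follow-up, using the existing criteria. Keep it separate from any record of shock as baseline status.
- In the coronary obstruction definition, replace the reference to the TAVI procedure with the index procedure (TAVI or SAVR).

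Align the CEC charter with both, and have everyone who classifies these events apply the same rule in both arms. Check already reported shock and coronary-obstruction events consistently under the new wording.

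The cost is a protocol amendment under section N and a limited re-review of reported events. Changing an endpoint definition during an open-label trial needs care, so the rule should be fixed in writing before the re-review and applied to every reported event regardless of arm. No added visits, tests or subjects are needed.

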## **CHRONIC RENAL INSUFFICIENCY**

Kidney damage or glomerular filtration rate (GFR) <60 mL/min/1.73 m^2 for or ≥3 months. Kidney damage is defined as pathologic abnormalities or markers of damage, including abnormalities in blood or urine test or imaging studies.

## **CONDUCTION DISTURBANCE REQUIRING PERMANENT PACEMAKER IMPLANTATION**

ACC/AHA 2006 Guidelines for the Management of Patients with Valvular Heart Disease (published in the August 1, 2006, issues of Journal of the American College of Cardiology and Circulation)

Any disturbance in the cardiac electrical conduction system that meets the American College of Cardiology (ACC)/American Heart Association (AHA)/ Heart Rhythm Society (HRS) Class I or IIa Guidelines for Device-Based Therapy of Cardiac Rhythm Abnormalities for Acquired Atrioventricular Block in Adults or Permanent Pacing in Chronic Bifascicular Block.

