### **Post-Procedure Pacing Guidelines**

- All patients should stay on telemetry until discharge
- Maintain temporary pacing until at least 48 hours post-implant in Cardiovascular Intensive Care Unit (CV-ICU) or local equivalent
- After 48 hours, obtain ECG and assess patient rhythm and conduction
- Based on assessment, and with the consult of an electrophysiologist as needed, take one of the following actions:
  - Discontinue temporary pacing
  - Continue temporary pacing for another 24 hours (longer if needed) to make further assessments
  - Place a permanent pacemaker according to ACC/AHA/HRS Guidelines for Device-Based Therapy of Cardiac Rhythm Abnormalities (Class I or IIb for Acquired Atrioventricular Block in Adults or Permanent Pacing in Chronic Bifascicular Block) as outlined in **Appendix R.13**
  - Prior to the permanent pacemaker implantation, document the reason for the placement of the permanent pacemaker via a 12-lead ECG
  - For complete heart block, review patient medications
  - Consider withholding some medications to assess for patient's intrinsic rate and conduction
  - If heart block persists off medications, a permanent pacemaker should be considered
  - If a permanent pacemaker is required, a dual chamber system is recommended to optimize patient hemodynamics
  - For additional information refer to the Pacing Guidelines in **Appendix R.13**

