- Valve-related dysfunction requiring repeat procedure (BAV, TAVI, or SAVR)
- All-cause death

Early safety composite endpoint-incidence estimates will be provided for the two treatment groups at 30 days. The statistical method will be the Bayesian version of a comparison of proportions.

5. Incidence of Clinical Efficacy (after 30 days) at 6 months, 12 months, 18 months, 24 months and annually thereafter up to 5 years. Clinical efficacy defined as a composite of:
- All-cause mortality
  - All stroke (disabling and non-disabling)
  - Requiring hospitalizations for valve-related symptoms or worsening congestive heart failure
  - NYHA class III or IV
  - Valve-related dysfunction (mean aortic valve gradient  $\geq 20$  mmHg, EOA  $\leq 0.9$ - $1.1$   $\text{cm}^2$  and/or DVI  $< 0.35$  m/s, AND/OR moderate or severe prosthetic valve regurgitation\*)

Clinical efficacy estimates will be provided for the two treatment groups at 6 months, 12 months, 18 months, 24 months and annually thereafter up to 5 years. The statistical method will be the Bayesian version of a comparison of proportions (with predictions).

\*Refers to VARC-2 definitions

6. Incidence of Time-Related Safety at 30 days, 6 months, 12 months, 18 months, 24 months and annually thereafter up to 5 years. Time-Related Safety defined as a composite of:
- Structural valve deterioration:
    - Valve-related dysfunction (mean aortic valve gradient  $\geq 20$  mmHg, EOA  $\leq 0.9$ - $1.1$   $\text{cm}^2$  and/or DVI  $< 0.35$  m/s, AND/OR moderate or severe prosthetic valve regurgitation\*)
    - Requiring repeat procedure (TAVI or SAVR)
  - Prosthetic valve endocarditis
  - Prosthetic valve thrombosis
  - Thromboembolic events (eg. stroke)
  - VARC bleeding, unless clearly unrelated to valve therapy (eg. trauma)

Time related safety composite endpoint-incidence estimates will be provided for the two treatment groups at 30 days, 6 months, 12 months, 18 months, 24 months and annually thereafter up to 5 years. The statistical method will be the Bayesian version of a comparison of proportions (with predictions).

\*Refers to VARC-2 definitions

7. Conduction disturbance requiring permanent pacemaker implantation at 30 days, 6 months, 12 months, 18 months, 24 months, and annually thereafter up to 5 years.

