### C.6.10 Multiplicity Considerations

It is recognized that with a multiplicity of tests comes inflation in the chance of a false finding of superiority or non-inferiority. Therefore, for the purpose of seeking approved labeling claims on designated secondary objectives, the following standard will be used: If the primary objective demonstrates non-inferiority, claims will be sought for selected secondary non-inferiority and superiority objectives and for superiority on the primary objective metric. These will be tested via a hierarchical (sequential) order that preserves the overall study-wise type I error rate at the level of 0.05, while requiring all non-inferiority tests to meet a nominal type I error rate of 0.05 and all superiority tests to meet a nominal type I error rate of 0.025. The testing order is specified below. The following objectives are tested in order, and testing continues if and only if all previous objectives have met their designated success criterion.

1. Primary endpoint (non-inferiority)
2. Transvalvular mean gradient at 12 months (non-inferiority)
3. Effective orifice area at 12 months (non-inferiority)
4. Change in NYHA classification from baseline to 12 months (non-inferiority)
5. Change in KCCQ score from baseline to 30 days (non-inferiority)

All of the above are non-inferiority tests and are tested with a type I error standard of 0.05. If all of the above tests meet their success criterion, the type I error rate of 0.05 that is passed on from the above tests will be split equally (using a Bonferroni justification) between the following parallel subfamilies, so that each subfamily is tested using a type I error rate of 0.025:

Subfamily #1: Primary endpoint (superiority)

Subfamily #2: Secondary (superiority) objectives #5–#18 as enumerated below, tested in ordered sequence such that all  $\alpha$  is passed on to subsequent tests if a test criterion is met, while all testing stops if a test criterion is not met. This procedure controls the type I error rate of this subfamily at the level 0.025.

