where  $\pi_{TAVI}$  and  $\pi_{SAVR}$  denote the proportion of subjects with moderate/severe aortic insufficiency at the discharge echo. The posterior probability  $P(H | \text{data})$  will be calculated and compared to a threshold of 0.975. The statistical method will be the Bayesian version of a comparison of proportions (see Section C.11).

18. New pacemaker implant rate for TAVI at 30 days or hospital discharge, whichever is longer (secondary objective #7). The hypothesis of interest is

$$H: \pi_{TAVI} < 30\%$$

where  $\pi_{TAVI}$  denote the binary rate of new pacemaker implants for TAVI at 30 days or hospital discharge (if longer). The posterior probability  $P(H | \text{data})$  will be calculated and compared to a threshold of 0.975. The statistical method will be the Bayesian version of a comparison of proportions (see Section C.11).

Other than the hierarchical testing procedure described above, no further multiplicity adjustments will be made in the analyses of the secondary endpoints. Summary data from other secondary objectives, such as device success and procedural success from secondary objectives #20 and #21, respectively, may be provided in the device labeling. However, no claims of statistical significance or other statistical inference will be made.

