**PERMANENT PACEMAKER IMPLANTATION**

Implantation of permanent pacemaker after the index procedure due to occurrence of conduction disturbances.

- **Procedure-related:** Permanent Pacemaker is implanted in subjects with new onset conduction disturbances or worsening of existing conduction disturbances
- **Not related to procedure:** Permanent Pacemaker is implanted in subjects with known conduction disturbances that did not advance after the index procedure.

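### The pacing instructions and the pacemaker endpoint definition name different guideline classes, and the plan does not say which definition objective #7 and labeling test #18 count

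*Combined protocol and SAP*

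**What the plan says.** Four places bear on the pacemaker count.

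- **Instructions to sites.** The Post-Procedure Pacing Guidelines in C.4.7.1 (TAVI) and C.4.7.2 (SAVR) carry the same text. One of the listed actions is to place a permanent pacemaker under "Class I or IIb for Acquired Atrioventricular Block in Adults or Permanent Pacing in Chronic Bifascicular Block". Both refer to Appendix R.13 for detail.
- **O.2, conduction-disturbance definition.** The disturbance must meet "Class I or IIa Guidelines for Device-Based Therapy of Cardiac Rhythm Abnormalities", for the same two groups of indications.
- **O.2, implantation definition.** A separate entry reads "Implantation of permanent pacemaker after the index procedure due to occurrence of conduction disturbances". It names no guideline class.
- **Endpoints.** Secondary objective #7 in C.6.8.1 opens with "Conduction disturbance requiring permanent pacemaker implantation at 30 days" and carries the name of the class-limited term. It is compared between arms and reported separately for new-onset and pre-existing disturbance. Test #18 in C.6.10.1 is headed "New pacemaker implant rate for TAVI at 30 days or hospital discharge, whichever is longer (secondary objective #7", but its parameter is said to "denote the binary rate of new pacemaker implants for TAVI at 30 days or hospital discharge (if longer". The goal is a rate below 30%, with the posterior probability "compared to a threshold of 0.975".

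**The concern.** The instruction and the class-limited definition share only Class I. A pacemaker placed for a IIb-only indication follows the instruction but falls outside the term that names #7. C.5.3 has the events committee classify endpoints by the protocol's definitions, so applying that term to #7 is the natural reading. The cross-reference to #7 may then carry it into #18.

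Two things are at stake. One is the reported pacemaker rate for #7 and its comparison between arms. The other is a labeling test against a fixed goal, where leaving out permitted implants would make the tested rate lower than the rate of pacemakers actually implanted. C.4.5 states that randomization is not blinded, so a definition left open can be chosen after the data are visible.

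**Working it through.** **1. Class named in each place**

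| Place | Class named | Limits the count? |
|---|---|---|
| C.4.7.1 and C.4.7.2, pacing instructions | I or IIb | Not a counting rule |
| O.2, conduction-disturbance term | I or IIa | Yes |
| O.2, implantation term | none | No |
| C.6.8.1, objective #7 | none; uses the name of the class-limited term | By name, yes |
| C.6.10.1, test #18 | none; cites #7, describes new implants | Open |

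**2. The plan's own figure behind the N**

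C.6.5.2 states no power or expected rate for #18. The only computed figure is the primary-endpoint sample size, which reproduces. The Farrington-Manning formula per arm is n = [(z₀.₉₅·s₀ + z₀.₉₅·s₁)/δ]², with δ = 0.07 and both rates 0.17.

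- Restricted estimates under the null are 0.2105 and 0.1405, so s₀ = √(0.2105×0.7895 + 0.1405×0.8595) = 0.536.
- s₁ = √(2×0.17×0.83) = 0.531.
- n = [1.645×(0.536 + 0.531)/0.07]² ≈ 629 per arm, or 1258 in total, as stated.
- 1258/0.94 gives 1339, and 1339/(1 − 0.125) gives 1531, also as stated. The plan then takes 1600.

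This figure is not in dispute. With 1:1 allocation it gives 1600/2 = 800 TAVI subjects for #18, or 1400/2 = 700 if the tests are run at the interim look.

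**3. Pass boundary for #18**

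The Beta(1,1) prior is stated for the primary endpoint and assumed here for #18. With x events in n subjects the posterior is Beta(1 + x, 1 + n − x), and #18 passes if P(π < 0.30 | x) > 0.975. The largest passing count is 214 of 800 (26.75%) or 186 of 700 (26.6%).

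**4. Chance of passing if some implants are not counted**

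Let p be the true all-implant rate and f the share of implants left out. The documents give no class mix, so f is an assumption, ranged from 0 to 20%. The counted events follow Binomial(n, p(1 − f)), and the chance of passing is P(X ≤ 214) for n = 800 or P(X ≤ 186) for n = 700. At p = 0.30:

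| f | Counted rate 0.30(1 − f) | n = 800 | n = 700 |
|---|---|---|---|
| 0 | 0.300 | 0.024 | 0.025 |
| 2% | 0.294 | 0.053 | 0.054 |
| 5% | 0.285 | 0.145 | 0.138 |
| 10% | 0.270 | 0.455 | 0.418 |
| 15% | 0.255 | 0.803 | 0.757 |
| 20% | 0.240 | 0.968 | 0.948 |

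**5. Other true rates, n = 800**

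- p = 0.32: 0.0007 with none left out, 0.013 with 5%, 0.107 with 10%.
- p = 0.35: 0.002 with 10%. Larger shares reach further: 0.034 with 15% and 0.228 with 20%.
- p = 0.20 or 0.15: about 1.0 whether 0 or 10% is left out.

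**6. Position of #18**

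C.6.10 puts #18 last in its subfamily. It is reached only after the primary non-inferiority test, tests #1 to #4 and tests #5 to #17 have all passed: 1 + 4 + 13 = 18 tests.

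**The case against.** The strongest reply is that #18 already says what it counts. Its title and its parameter speak of new pacemaker implants, and O.2 defines implantation with no class limit. On that reading nothing is left out and the chance of passing at a true 30% stays at 0.024 to 0.025. This largely stands. A reader might infer that #18 counts only Class I or IIa implants, but the documents do not establish that; the only route is the reference to #7. The reply does not rescue #7, whose name matches the class-limited term, and it leaves two competing definitions with no rule for choosing between them.

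A reader might also infer from step 4 that the plan violates its requirement for "all superiority tests to meet a nominal type I error rate of 0.025". That does not follow. If the endpoint were the Class I or IIa rate, testing that rate against 30% would hold its nominal error. The issue is which quantity is measured; the table shows what happens if the result is read as an all-implant rate.

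The mismatch also runs both ways: the definition includes IIa, which the instructions do not name. Finally, Appendix R.13 and the detailed SAP text were not available for this check and may settle the point. The protocol wording would still need correcting.

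**Conclusion.** The contradiction in class wording is certain and applies to both arms. Read literally, a IIb-only implant is permitted but not counted in #7. For #18 the finding is narrower: the governing definition is unstated.

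If the class-limited definition were applied to #18, the chance of passing at a true all-implant rate of 30% with 800 TAVI subjects would rise from 0.024 to 0.053, 0.145 or 0.455 for assumed shares of 2%, 5% or 10% left out. This rests on that definition being used, a true rate near 30%, the assumed shares and the assumed Beta(1,1) prior.

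These figures are not the probability of a wrong labeling claim, because #18 is tested only if all earlier tests pass. For shares up to 10% the effect has almost gone by a true rate of 35%, and at 20% or below #18 passes either way. The primary endpoint is not affected.

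**What to change.** State in C.6.8.1, C.6.10.1 and the SAP that #7 and #18 count every new permanent pacemaker implanted after the index procedure for a conduction disturbance, whatever the guideline class. This is the O.2 implantation definition. Keep the new-onset and pre-existing split already planned for #7, and report guideline class as a breakdown.

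Separately, C.4.7.1, C.4.7.2, the O.2 conduction-disturbance definition and Appendix R.13 must be reconciled on class. That is for the clinical leads to settle; no view is taken here on which class is right.

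The cost is wording in the protocol and SAP, plus recording the guideline class for each implant if the case report form does not already do so. The reported pacemaker rate may be somewhat higher than under a class-limited count. Sample size and the primary analysis do not change.
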